## Follow up time points

Subjects with OA knee will be recruited into this randomized controlled trial. Baseline assessments including KOOS, IPAQ, muscle strength, posture control and serum markers will be taken before PEMF treatments, and same set of measurements will be monitored at 1- and 2- months after the commencement of PEMF, and at 3-, 6- and 12- months after finish the PEMF intervention if possible.

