## Sample size calculation:

KOOS Score will be employed as primary outcome for sample size estimation. The minimal clinically important change has been determined as 10 for KOOS (21). A repeated ANOVA will be used to compare KOOS scores, IPAQ, muscle strength, posture control and serum markers before PEMF treatment and at 1-, 2-months after the commencement of PEMF treatment, and at 3-, 6- and 12- months after finish the intervention. When the sample size is 34 per groups with 6 repeated measurements, a one-way analysis of variance will have 95% power to detect at the 0.05 level and change of 10 with a standard deviation of 15 KOOS score (22). An additional 35% will be added to account for possible attrition. Thus, 110 (55x2) subjects will be recruited in total.

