### Data processing and analysis:

The data obtained in the tests will be analysed using Statistical Package for Social Science (SPSS) (IBM SPSS ver.26). For parametric data, paired sample t test will be used. Wilcoxon signed rank test will be used to analyse the data sets if they are non-parametric. The alpha level will be set at 0.05 for all statistical tests.

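### Run in its standard form, the repeated ANOVA over six visits keeps only patients with every visit, which fits badly with 35% expected attrition and optional late visits

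*Protocol*

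**What the plan says.** The Protocol's Sample size calculation section names the analysis: "A repeated ANOVA will be used to compare KOOS scores", together with the other outcomes, at baseline and at five later times. These are 1 and 2 months after treatment starts and 3, 6 and 12 months after it ends. The sizing uses the same structure: "When the sample size is 34 per groups with 6 repeated measurements", with "a one-way analysis of variance will have 95% power" to detect an effect "at the 0.05 level and change of 10 with a standard deviation of 15 KOOS score". It continues "An additional 35% will be added to account for possible attrition", which gives 55 per arm and 110 in total.

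The Follow up time points section places the last three assessments "at 3-, 6- and 12- months after finish the PEMF intervention if possible".

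The Data processing and analysis section names the software ("The data obtained in the tests will be analysed using Statistical Package for Social Science (SPSS) (IBM SPSS ver.26") and then paired t tests, or Wilcoxon signed rank tests for non-parametric data. It does not mention the repeated ANOVA. No section names a mixed model, imputation or another way to keep a patient with a missed visit. No section says that incomplete patients are excluded.

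**The concern.** A classical repeated-measures ANOVA needs a value at every time point for each patient, and the SPSS procedure of that name removes any patient with a gap. The Protocol expects a third of its patients to be lost and treats half of the six assessments as optional. The on-treatment comparison would then depend on attendance up to a year after treatment ended.

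Two things are at stake. The first is precision, because data already collected at 1 and 2 months would go unused. The second, and more important, is the comparison itself. Completers are selected after randomisation. If patients who are doing badly tend to leave, and one arm does better, the two arms lose different patients even when the dropout rule is the same in both.

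**Working it through.** **Inputs from the Protocol.** 34 per group, six measurements, change 10, SD 15, alpha 0.05, power 95%, attrition 35%, 55 per arm. **Assumed, because not stated:** two-sided test; correlation between visits 0.5; the rates of missed visits and the dropout mechanism used below.

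**1. The Protocol's own figure.** For the between-group effect of a repeated-measures ANOVA with two groups, f = 10/(2 x 15) = 0.333 and the noncentrality is N f² m / (1 + (m - 1)rho). With N = 68, m = 6 and rho = 0.5:

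68 x 0.1111 x 6 / 3.5 = 12.95, on 1 and 66 degrees of freedom, giving power 94.4%.

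So 34 per group at about 95% is reproduced at rho near 0.5. The same formula gives 98.7% at rho 0.3 and 84.3% at rho 0.8.

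**2. The attrition allowance.** 34/(1 - 0.35) = 52.3, so 53 per arm; the stated 55 is within two patients. Inflating so that about 34 remain is the logic of an analysis of completers. Applied to 55 per arm:

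55 x 0.65 = 35.75 complete per arm, against 34 needed; power about 95% (n = 35, rho 0.5).

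The margin is one or two patients per arm. About 38 of the 110 patients would not enter the analysis.

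**3. Optional visits missed by patients who otherwise stay.** If a share q of the remaining patients misses each of the three late visits, complete patients per arm = 35.75 x (1 - q)³.

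| q (assumed) | Complete per arm | Power (rho 0.5, n rounded down) |
|---|---|---|
| 0 | 35.75 | 95% |
| 5% | 30.7 | 91% |
| 10% | 26.1 | 87% |
| 20% | 18.3 | 72% |

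**4. Observed data left unused.** If the 35% attrition builds up evenly over the five later visits (assumed), the share still observed at the six visits is 1, 0.93, 0.86, 0.79, 0.72 and 0.65, a mean of 82.5%. Deletion of incomplete patients uses 65%. The gap is 17.5% of 660 planned patient-visits, or about 115.

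**5. Bias from selection.** Simulation: true difference 10 at month 2, SD 15, correlation 0.5, and 35% overall dropout after month 2. Dropout is logistic in the month-2 score with the same rule in both arms, lower scores leaving more often. A repeated ANOVA tests arm by time, so the relevant quantity is the difference between arms in change from baseline to month 2.

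| Odds of leaving, per SD lower score | Dropout, sham / PEMF | Completers' difference in change | All observed month-2 data |
|---|---|---|---|
| 1.6-fold | 38% / 31% | 9.7 | 10 |
| 2.7-fold | 41% / 29% | 9.2 | 10 |
| 7.4-fold (extreme) | 44% / 26% | 8.4 | 10 |

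The estimate is pulled towards no effect by about 0.3, 0.8 and 1.6 points.

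**The case against.** The strongest reply is that the Protocol never says incomplete patients are dropped. The repeated ANOVA appears only in the sample size paragraph, where the term is often loose shorthand, and the analysis section names paired tests. A paired test at month 2 needs two visits, so under that section a missed 12-month visit removes nobody. An SAP that is not at hand could also settle missing data. This stands to the extent that deletion is an inference and confidence should be medium. It does not remove the point. The repeated ANOVA is the only multi-visit analysis named, it is stated as what will be used, and an SAP that did otherwise would conflict with it.

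A second reply is that the sample size already budgets for completers. That is right for pure dropout: 35.75 exceeds 34. A reader might infer that the trial is underpowered because of its attrition, and the documents do not support that. Power falls only if patients miss optional visits on top of the 35%. Nor do the documents support a scenario of 10% or 15% missing independently at each of five visits. It would leave 1 - 0.90⁵ = 41% or 1 - 0.85⁵ = 56% of patients incomplete, more than the Protocol expects.

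A third reply concerns the size of the bias. Comparing raw month-2 means among completers in the same simulation gives about 9.5, 8.5 and 6.9, and a reader might quote those. They overstate the harm, because the named method tests differences in change. Under this mechanism the bias is also attenuation; no risk of a false positive is shown.

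**Conclusion.** The point holds in a limited form. The Protocol names a method that, run in the standard way, suits neither its expected attrition nor its optional visits, and its two statements of the analysis disagree.

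Planned power survives 35% pure dropout with a margin of one or two patients per arm. Beyond that, about 31, 26 or 18 per arm would be complete if 5%, 10% or 20% of those remaining missed each optional visit. The main harm is the selected comparison. It loses about 0.3 to 0.8 of a true 10 points under the two milder dropout assumptions and about 1.6 under an extreme one, always towards no effect.

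These sizes rest on an assumed correlation of 0.5 and on assumed missed-visit rates and dropout strengths; the Protocol gives none of them. That patients will in fact be deleted follows from the named method and not from any sentence in the Protocol. The change is worth making, with medium confidence.

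**What to change.** In the Sample size calculation section, replace the repeated ANOVA with a linear mixed model for repeated measures, fitted with SPSS MIXED. Include all randomised patients and all observed visits, with arm, visit as a categorical factor, arm by visit, and baseline KOOS. Late visits then add information where they occur and remove nobody where they do not. Bring the Data processing and analysis section into line by naming the same model there as the between-arm analysis. Which visit carries the primary contrast is a separate choice that the Protocol has not made, and this change does not depend on it.

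The cost is amended wording and slightly more programming in software already named, with no extra patients or visits. The model relies on data being missing at random, a weaker assumption than a completers' analysis needs.

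### Baseline KOOS is one of the six outcome measurements in the repeated ANOVA and is not used as a covariate; whether the stated 95% power holds depends on an unnamed test and an unstated correlation

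*Protocol*

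**What the plan says.** The protocol's section on sample size calculation makes KOOS the primary outcome. It compares scores by repeated ANOVA "before PEMF treatment and at 1-, 2-months after the commencement of PEMF treatment" and again "at 3-, 6- and 12- months after finish the intervention". That is one baseline and five later assessments, which matches the count in "When the sample size is 34 per groups with 6 repeated measurements". The section on follow-up time points confirms that KOOS belongs to the baseline set and that the "same set of measurements will be monitored at 1- and 2- months after the commencement of PEMF", with the three later visits to be held where possible.

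The power statement reads "a one-way analysis of variance will have 95% power", for a change of 10 KOOS points with a standard deviation of 15. It does not say whether the test is of arm, of time or of their interaction, and it gives no correlation between visits. Baseline appears nowhere as a covariate. The section on data processing and analysis names only the paired t test and the Wilcoxon signed rank test, and adds "The alpha level will be set at 0.05 for all statistical tests".

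**The concern.** Allocation is randomised 1:1, so a baseline score carries no treatment effect in expectation. As an outcome it adds a visit at which the true arm difference is zero. As a covariate it would explain part of the variation in later scores.

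Two between-arm tests are available in the planned model. The arm main effect averages over all six measurements and so mixes the zero at baseline with the effect at the other five. The arm-by-visit interaction uses baseline as a reference and removes stable differences between patients, but spreads the question over five degrees of freedom. At stake is whether 34 completers per arm give the advertised 95% power. If they do not, a real 10-point benefit could be missed more often than the sponsor expects, although the baseline data that could help are already being collected.

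**Working it through.** **Inputs from the protocol** (sample size section): n = 34 per arm; six measurements; change 10; SD 15, so variance 225; level 0.05; stated power 95%.

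**Assumptions:** two-sided testing; 15 is the SD of a single score; equal correlation ρ between any two visits, shown at 0.3, 0.5 and 0.7; unless stated otherwise, a true arm difference of 0 at baseline and 10 at all five later visits. Power comes from the noncentral F distribution. For one-degree-of-freedom contrasts λ = (n/2) × difference² / variance, with 1 and 66 df.

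**1. The plan's own figure.** The variance of a six-visit mean is 225(1 + 5ρ)/6, which is 131.25 at ρ = 0.5. With a 10-point difference at all six measurements, baseline included, λ = 17 × 100/131.25 = 12.95 and power is 94.4%, close to the stated 95%. A paired t test on 34 patients also comes close: noncentrality (10/15)√34 = 3.89, power 96.5%. An unadjusted two-arm comparison at one visit does not: λ = 17 × 100/225 = 7.56, power 77%.

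**2. Arm main effect with no difference at baseline.** The averaged effect is 5 × 10/6 = 8.33. At ρ = 0.5, λ = 17 × 69.44/131.25 = 8.99 and power is 84.0%. Reaching 95% would need 51 per arm.

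**3. Arm-by-visit interaction.** The squared deviations of the six differences from their mean sum to 8.33² + 5 × 1.67² = 83.3. At ρ = 0.5, λ = 17 × 83.3/(225 × 0.5) = 12.59 on 5 and 330 df, and power is 78.4%. Reaching 95% would need 54 per arm.

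**4. Adjusted difference at 2 months.** The variance given baseline is 225(1 − ρ²), which is 168.75 at ρ = 0.5. Then λ = 1700/168.75 = 10.07 and power is 87.8%.

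**5. Adjusted mean of the five later visits.** The variance is 225[(1 + 4ρ)/5 − ρ²], which is 78.75 at ρ = 0.5. Then λ = 1700/78.75 = 21.59 and power is 99.6%.

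Power at 34 per arm, steady 10-point effect after baseline:

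| Test | ρ = 0.3 | ρ = 0.5 | ρ = 0.7 |
|---|---|---|---|
| Arm main effect, six visits | 93.8% | 84.0% | 74.1% |
| Arm-by-visit interaction, 5 df | 61.5% | 78.4% | 95.9% |
| 2 months, unadjusted | 77.3% | 77.3% | 77.3% |
| 2 months, adjusted for baseline | 81.0% | 87.8% | 96.6% |
| Five-visit mean, adjusted for baseline | 99.6% | 99.6% | 99.9% |

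**6. If the effect fades.** Suppose the difference is 10 at months 1 and 2 and 0 afterwards, with ρ = 0.5.
- Adjusted five-visit mean: the difference is 20/5 = 4, λ = 17 × 16/78.75 = 3.45, power about 45%.
- Interaction: the sum of squares is 2 × 6.67² + 4 × 3.33² = 133.3, λ = 17 × 133.3/112.5 = 20.15, power 95%.
- Adjusted 2-month difference: unchanged at 88%.

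With differences of 5, 10, 10, 5 and 0 at the five later visits, the same three figures are 78%, 86% and 88%.

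**The case against.** A repeated-measures ANOVA that includes baseline, tested through the group-by-time term, is a conventional and valid analysis. Choosing covariates and naming the tested term are often left to a statistical analysis plan, which may exist here. The correlation is not in the protocol, and the results turn on it: at ρ = 0.2 the main effect still has 97.4% power, and at ρ = 0.8 the interaction has 99.7%. If all 55 recruited per arm were retained, both would exceed 95% at ρ = 0.5 (96.6% and 95.4%).

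Most of this stands, and it limits the point. A reader might infer that the planned ANOVA dilutes the treatment effect whatever is tested. It does so only for the arm main effect; the interaction is not diluted, and its error term already excludes stable between-patient variance. A reader might also infer that a baseline covariate would by itself lift power above 99%. That figure belongs to the five-visit mean under an effect lasting to 12 months after an 8-week intervention, and the protocol gives no evidence of such persistence. At ρ = 0.3 the adjusted 2-month contrast (81%) has less power than the main effect under a steady effect (94%).

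The objection does not remove what the protocol itself fixes: baseline is counted among the six measurements, and the 95% is claimed on that count. The retention margin does not settle it either. The protocol allows for 35% attrition, which leaves 55 × 0.65 = 35.75, about 36 per arm. At ρ = 0.5 that gives 86% for the main effect and 81% for the interaction.

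**Conclusion.** The point holds in conditional form. Baseline KOOS is treated as an outcome, no adjustment for it is planned, and the protocol does not say which term carries the 95%. At ρ = 0.5, the between-arm main-effect calculation comes near that figure only by giving the arms a 10-point difference before treatment, which randomisation excludes in expectation. With that removed, main-effect power falls from 94% to 84%. On the interaction reading the shortfall is larger at low correlation, disappears at about 0.7, and shrinks or vanishes if the effect fades.

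These sizes rest on an assumed common correlation, an assumed effect profile, and reading 15 as the SD of a single score. A third reading, suggested by the paired tests in the data processing section, is that the 95% refers to change within patients. The figure is then roughly right but says nothing about PEMF against sham.

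**What to change.** Take baseline out of the outcome vector. Model the post-baseline KOOS scores on arm, visit, arm-by-visit and baseline KOOS, and name one between-arm contrast as primary.

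Restate the power for that contrast with a stated correlation and, if it averages over visits, a stated effect profile. At 34 per arm the adjusted 2-month difference has about 81%, 88% and 97% power at ρ = 0.3, 0.5 and 0.7. The adjusted five-visit mean should be chosen only if a sustained effect can be justified.

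Bring the data processing and analysis section into line, since the paired tests it names do not compare the arms.

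The cost is wording: baseline KOOS is already collected, and SPSS, the package named, can fit the model. The stated power may have to come down from 95%, or the sample size be revisited.

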# Objective:

To conduct a double-blinded, randomized controlled trial to investigate the effect of PEMF treatment on knee pain for patients with knee OA.

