### Subject recruitment:

The study protocol will be in compliance with Declaration of Helsinki and ICH-GCP. Subjects will be recruited from the Department of Orthopaedics and Traumatology of Prince Wales Hospital in Hong Kong and patients who can meet all the inclusion criteria will be invited to participate in two sessions of assessments.

A total of 110 subjects and 20 matched non-Knee OA subjects will be recruited and follow up for 8 weeks. They will undergo 1:1 randomization into two study arms:

- 1. PEMF treatment
- 2. Control (Sham treatment)

Inclusion criteria:

- 1. Age 50 or above
- 2. Unilateral knee OA with Kellgren-Lawrence grade 2-3 by X-ray
- 3. Sedentary lifestyle (Tegner activity level  $\leq$  3)
- 4. No acute knee injuries in past 12 months
- 5. No muscle strain in past 12 months
- 6. No degenerative joint diseases in other joints except the involved knee

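### The 95% power for 34 per group is not established for PEMF versus sham: no between-arm difference or within-subject correlation is stated

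*Protocol*

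**What the plan says.** The protocol has one sample size justification, under Sample size calculation. It starts from the outcome, "KOOS Score will be employed as primary outcome for sample size estimation", and the effect, "The minimal clinically important change has been determined as 10 for KOOS". The analysis is described as "A repeated ANOVA will be used to compare KOOS scores" and other measures between the pre-treatment assessment and the five later visits. The power claim assumes 34 patients in each group, six measurements per patient and an SD of 15. For that setting the section asserts: "a one-way analysis of variance will have 95% power to detect at the 0.05 level and change of 10". Allowing 35% for attrition, the total is 110, or 55 per arm.

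The section names no arm effect or arm-by-time effect and gives no correlation between a patient's repeated scores. Data processing and analysis names only within-patient tests: "For parametric data, paired sample t test will be used", with the signed-rank test as the alternative.

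The design is a two-arm comparison. The Objective is a "randomized controlled trial to investigate the effect of PEMF treatment on knee pain", and under Subject recruitment "They will undergo 1:1 randomization into two study arms", PEMF and sham.

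**The concern.** A power figure belongs to one test of one contrast. Here the contrast that randomisation protects is PEMF against sham, but the named test, the word used for the effect and the visits compared all describe change over time. A test of change within an arm has the same power whether or not the sham arm improves equally, so it says nothing about the chance of separating PEMF from sham.

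This is the only power figure for the primary outcome. A null result against sham would naturally be judged against it, and the text gives no way to verify that it applies to that comparison.

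**Working it through.** **Inputs from the protocol:** 34 per group, six measurements (one before treatment, five after), 10 points, SD 15, alpha 0.05, 55 per arm recruited, 35% attrition.

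**Assumptions:** two-sided testing; equal correlation ρ between any two visits, shown at 0.3 / 0.5 / 0.7; the full 10 points at each post-baseline visit. Powers are from noncentral t or F distributions.

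**Step 1. Reproduce 95%.** Three readings come close.

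- *Paired test within an arm, 15 as SD of change.* Noncentrality (10/15)·√34 = 3.89 on 33 df; power 96.5%.
- *One-way repeated measures over time within an arm, 15 as SD of a score.* For the profile 0, 10, 10, 10, 10, 10 the mean is 8.33 and the sum of squared deviations is 83.3. Then λ = 34 × 83.3 / [225(1 − ρ)] = 18.0 / 25.2 / 42.0 on 5 and 165 df; power 92 / 98 / >99%, reaching 95% at ρ = 0.38.
- *Two-group comparison of the mean of six measurements, 10 points at all six.* The SD of the mean is 15·√[(1 + 5ρ)/6], which is 11.46 at ρ = 0.5; power is 94.4% there and 95.0% at ρ = 0.477.

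The first two do not involve sham. The third does, but it needs the arms to differ by 10 points before treatment, whereas randomisation gives an expected baseline difference of zero.

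**Step 2. Between-arm power at 34 per arm, arms equal at baseline, score SD 15.**

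| Contrast | Calculation | ρ = 0.3 | 0.5 | 0.7 |
|---|---|---|---|---|
| One visit, unadjusted (also a two-arm one-way ANOVA) | noncentrality 10/(15·√(2/34)) = 2.75, 66 df | 77% | 77% | 77% |
| One visit, baseline-adjusted | SD 15·√(1 − ρ²) = 14.3 / 13.0 / 10.7 | 81% | 88% | 97% |
| Arm-by-time interaction | λ = (34/2) × 83.3 / [225(1 − ρ)] = 9.0 / 12.6 / 21.0; 5 and 330 df | 61% | 78% | 96% |
| Six-measurement main effect | difference 50/6 = 8.33; SD 9.7 / 11.5 / 13.0 | 94% | 84% | 74% |
| Baseline-adjusted mean of five post-baseline visits | SD 15·√[(1 + 4ρ)/5 − ρ²] = 8.9 / 8.9 / 7.8 | >99% | >99% | >99% |

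The single unadjusted visit would need 60 per arm for 95%.

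**Step 3. Retained numbers.** 55 × 0.65 = 35.75, about 36 per arm.

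- One visit: 80% unadjusted; 83 / 90 / 97% baseline-adjusted.
- Baseline-adjusted mean of the 1- and 2-month visits, SD 15·√[(1 + ρ)/2 − ρ²] = 11.2 / 10.6 / 9.0: 96 / 98 / >99%, if 10 points holds at both.
- Baseline-adjusted mean of all five visits: >99% throughout if the average difference is 10, but 91 / 91 / 96% if it is 7.

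**The case against.** The strongest reply is that no arithmetic error is shown. The text refers to groups and to 55 × 2 patients, so an ordinary between-arm formula on six measurements could be the source of 95%, with a correlation just under 0.5. The wording also attaches 15 to a KOOS score, so its plain meaning is the SD of a score, and the paired reading strains that wording. The choice of contrast and baseline adjustment may be set out in an analysis plan that is not at hand. Finally, nothing in recruitment or analysis depends on the 95% label.

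Much of this stands. A reader might infer that the trial was deliberately powered on a within-arm test; the text does not establish that. A reader might also infer that the SD of 15 has no meaning; score SD is the natural reading and is used above. Nor is 95% impossible for a between-arm test.

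What does not stand is the conclusion that only detail is missing. The between-arm formula that returns 95% needs the treatment difference to exist before treatment. The protocol itself makes the power claim, so a separate analysis plan cannot be assumed to repair it.

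**Conclusion.** The concern holds in a limited form: 95% power at 34 per group is not established for PEMF versus sham. It matches either a within-arm test of change or a between-arm formula that assumes a 10-point difference at baseline. With arms equal at baseline, between-arm power runs from 61% to above 99% across the contrasts and correlations shown. The two between-arm tests that a repeated-measures ANOVA offers have 78% (interaction) and 84% (main effect) at correlation 0.5.

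It is tempting to conclude that 110 patients are too few. The documents do not support that: a baseline-adjusted mean over visits exceeds 95% at 34 per arm, and even a single baseline-adjusted visit has about 90% with 36 retained at correlation 0.5.

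The figures rest on score SD 15, equal correlation between visits, an assumed correlation of 0.3 to 0.7 and a constant post-baseline difference. Only the unadjusted single-visit 77% and the paired 96.5% need no correlation.

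**What to change.** Keep 110. Delete the sentence that attributes 95% power to a one-way ANOVA. Name one baseline-adjusted between-arm KOOS contrast and its visit or visits, and restate power for it with the difference, SD, alpha, correlation and retained number.

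For a single named visit, the text could read:

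> With about 36 per arm retained (55 × 0.65), a 10-point PEMF-minus-sham difference in KOOS at [named visit] (SD of score 15, two-sided alpha 0.05) has about 80% power unadjusted and about 90% baseline-adjusted at an assumed correlation of 0.5 (83% to 97% for 0.3 to 0.7).

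If a mean over visits is preferred, list the visits and give the same inputs. For the 1- and 2-month visits, 36 per arm gives 96 / 98 / >99% at correlation 0.3 / 0.5 / 0.7, provided the 10-point difference holds at both. Do not claim more than 95% for an unnamed set of visits. For all five, that needs an average difference of 10 points, including visits that the Follow up time points section makes conditional on feasibility; power falls to about 91% at correlation 0.3 to 0.5 if the average is 7.

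The cost is one rewritten paragraph and a decision on the contrast. No patients are added, but the stated power may be less favourable.
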